1.2.1.2.1 Clinical safety of ribociclib

Clinical safety of ribociclib with endocrine agents such as letrozole, tamoxifen, exemestane and fulvestrant has been evaluated in several phase I and III combination trials. The recommended dose of ribociclib in combination with these agents was declared as 600 mg qd on a 3 weeks on/1 week off schedule.

The safety profile of ribociclib in combination with letrozole was investigated in a randomized clinical trial of ribociclib and letrozole versus placebo and letrozole (CLEE011A2301) in 668 treatment-naive postmenopausal women with HR-positive, HER2-negative, advanced BC. Most common treatment-emergent AEs reported in the ribociclib arm in this study occurring in >30% of patients were neutropenia (74.3%), nausea (51.5%), infections (50.3%), fatigue (36.5%), diarrhea (35.0%), alopecia (33.2%) and leukopenia (32.9%). The most common grade 3 or 4 AEs reported in \geq 5 % of patients in the ribociclib arm were neutropenia (59.3%), leukopenia (21.6%), hypertension (9.9%), increased alanine aminotransferase (9.3%), lymphopenia (6.9%) and increased aspartate aminotransferase (5.7%). Febrile neutropenia occurred in 1.5% of the patients in the ribociclib arm. Blood creatinine increases were reported in 6.9% of patients. Four patients (1.2%) met the biochemical and clinical criteria for Hy's Law with 3 reported as treatment-related and all 4 returning to normal values after treatment

discontinuation. Eleven patients (3.3%) presented on treatment QTcF prolongation >480 msec. Serious AEs were reported in 21.3% of patients in the ribociclib arm with 7.5% of serious AEs deemed by investigators as treatment-related. There were 3 fatal events in the ribociclib arm (disease progression, sudden death, unknown cause) with 1 AE (sudden death) reported as treatment-related in a patient that had grade 3 hypokalemia and grade 2 QTcF prolongation (483 msec). Neutropenia, QT interval prolongation and hepatobiliary toxicity are considered to be important identified risks for ribociclib which appear to be manageable and reversible with adequate monitoring, interruption and/or reduction of ribociclib dosing.

For a comprehensive review of safety profile of ribociclib in combination with endocrine agents refer to the most recent ribociclib [Investigator's Brochure].

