6.3.1.3.5 Guidance for all other adverse reactions

Consider performing an analysis of serum potassium, calcium, and magnesium for all adverse reactions that are potentially associated with electrolyte imbalance. If electrolyte values are outside of the normal range, interrupt ribociclib administration, correct electrolytes with supplements or appropriate therapy as soon as possible, and repeat electrolyte testing until documented normalization of the electrolytes.

For all other adverse events, including Toxic Epidermal Necrolysis (TEN), which is a grade-4 event by CTCAE, please follow recommendations in Table 6-7.

Table 6-7Ribociclib dose reduction/interruption and managementrecommendation for all other adverse reactions

Grade	Dose Adjustment and Management Recommendations
1	No dose adjustment recommended. Initiate appropriate medical therapy and monitor.
2	Dose interruption until recovery to grade ≤ 1 . Initiate appropriate medical therapy and monitor. Re-initiate ribociclib at the same dose. If the same toxicity recurs at grade 2, interrupt ribociclib until recovery to grade ≤ 1 . Re-initiate ribociclib at the next lower dose level.

Novartis	Confidential	Page 65
Amended Protocol Version 04 (Clean)		Protocol No. CLEE011A2404

3	Dose interruption until recovery to grade ≤1. Initiate appropriate medical therapy and monitor. Re-initiate ribociclib at the next lower dose level. If toxicity recurs at grade 2: temporary dose interruption until recovery to grade ≤1 and reduce ribociclib dose the next lower dose level. If toxicity recurs at grade 3, discontinue ribociclib.
4	Discontinue ribociclib and treat with appropriate medical therapy.

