7.1 Study flow and visit schedule

Table 7-1 lists all of the assessments and indicates with an "X", the visits when they are performed. All data obtained from these assessments must be supported in the patient's source documentation. The table indicates which assessments produce data to be entered into the clinical database (D) or remain in source documents only (S) ("Category" column).

Note:

- During screening visits, lab assessments including white blood cell (WBC) count, absolute neutrophil count (ANC), absolute lymphocyte count, hemoglobin, platelets, INR, ALT, AST, total bilirubin (or direct bilirubin if Gilbert's Syndrome), serum creatinine, electrolytes (potassium, sodium, calcium corrected for serum albumin, and magnesium) are required to be collected within 14 days of C1D1 for eligibility assessment.
- During treatment phase, only selected labs assessments are required to be collected in the clinical database at the patient scheduled visits: WBC, ANC, absolute lymphocyte count,

hemoglobin, platelets, AST, ALT, ALP, total bilirubin, and direct bilirubin (if clinically indicated). Electrolytes should be monitored at the beginning of each cycle before resuming ribociclib dose during the first 6 cycles and as clinically indicated thereafter. The results should not be captured in clinical database. Eventual abnormal electrolyte lab results should be reported as AEs at the investigator's discretion.

- ECG will be performed at screening (within 5 days of C1D1), C1D15, C2D1, then as clinically indicated, and EOT.
- If treatment is withheld at any time during the study, all study visits, safety assessments, and efficacy assessments should be adjusted accordingly to match the treatment cycles.
- For all visits, there is a +/-3 day window on assessments to take into account scheduling over public holidays, if not explicitly specified otherwise.

Novartis	
Amended Protocol Version 04 (Clean)	

Confidential

Table 7-1	Visit evaluation	schedule	(Core Phase)
-----------	------------------	----------	-------------	---

	Category	Reference to Protocol Section	Screening Phase	Core	Core Treatment Phase						End of study treatment (EOT) within 7 days from the last dose of study treatment	Safety follow up within 30 days of last dose of study treatment		
Visit name			Screening (-28 Days to Day 1)	C1D1	C1D15	C2D1	C2D15	C3D1	C4D1	C5D1	C6D1-C11D1	C12D1 and subsequent cycles (up to cycle 36)		
Screening														
Study Informed Consent	D	7	×											

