7.2.2.5 Laboratory evaluations

Local site laboratories will be used for the analysis of scheduled hematology, biochemistry, and other blood specimens collected as part of safety monitoring. All unscheduled blood testing will also be performed locally. The time windows granted for laboratory evaluations are identical to the corresponding visit time windows for each visit (refer to Section 7.1).

Laboratory abnormalities that are considered clinically significant, induce clinical signs or symptoms, require concomitant therapy or require dose adjustments in ribociclib treatment (see Section 8.1) constitute an adverse event (AE) and must be reported as an AE on the AE eCRF page.

Laboratory values obtained at the screening visit will be used to assess eligibility to meet Inclusion criteria. If patient meets all inclusion and no exclusion criteria, the screening labs can be used for baseline if patient is dosed within 14 days of the screening visit. If patient cannot be dosed within 14 days of screening, then the labs should be repeated the day before patient starts dosing (see baseline visit in Table 7-1).

Only selected laboratory parameters (see Table 7-5) will be collected on the eCRF.

Test Category	Test Name			
Hematology	WBC, ANC,	WBC, ANC, absolute lymphocyte count, hemoglobin, platelets		
Chemistry	Screening	ALT (SGPT), AST (SGOT), calcium corrected for serum albumin, creatinine c creatinine clearance, potassium, sodium, magnesium, total bilirubin (or direct bilirubin if Gilbert's syndrome)		
	Scheduled visits	Alkaline phosphatase, ALT (SGPT), AST (SGOT), total bilirubin, direct bilirubin (if clinically indicated)		
		Note: potassium, sodium, calcium corrected for serum albumin, and magnesium are to be monitored but are not captured in the eCRF. Abnormal electrolyte lab results should be reported as AEs at the investigator's discretion.		
Coagulation	International normalized ratio [INR]			
Pregnancy	Serum and Urine			

 Table 7-5
 Local Clinical laboratory parameters collection plan

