8.1.2 Laboratory test abnormalities

8.1.2.1 Definitions and reporting

Laboratory abnormalities that constitute an Adverse event in their own right (are considered clinically significant, induce clinical signs or symptoms, require concomitant therapy or require changes in study treatment), should be recorded on the Adverse Events eCRF. Whenever possible, a diagnosis, rather than a symptom should be provided (e.g. anemia instead of low hemoglobin). Laboratory abnormalities that meet the criteria for Adverse Events should be followed until they have returned to normal or an adequate explanation of the abnormality is found. When an abnormal laboratory or test result corresponds to a sign/symptom of an already reported adverse event, it is not necessary to separately record the lab/test result as an additional event.

Laboratory abnormalities that do not meet the definition of an adverse event should not be reported as adverse events. A Grade 3 or 4 event (severe) as per CTCAE does not automatically indicate a SAE unless it meets the definition of serious as defined below and/or as per investigator's discretion. A dose hold or medication for the lab abnormality may be required by the protocol in which case the lab abnormality would still, by definition, be an adverse event and must be reported as such.

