## 5.3 Laboratory parameters derivations

Grade categorization of lab values will be assigned programmatically as per NCI Common Terminology Criteria for Adverse Events (CTCAE) version 4.03. The calculation of CTCAE grades will be based on the observed laboratory values only, clinical assessments will not be taken into account. The criteria to assign CTCAE grades are given in Novartis internal criteria for CTCAE grading of laboratory parameters. The latest available version of the document based on the underlying CTCAE version 4.03 at the time of analysis will be used. For laboratory tests where grades are not defined by CTCAE v4.03, results will be graded by the low/normal/high (or other project-specific ranges, if more suitable) classifications based on laboratory normal ranges.

A severity grade of 0 will be assigned for all non-missing lab values not graded as 1 or higher. Grade 5 will not be used. For laboratory tests that are graded for both low and high values, summaries will be done separately and labelled by direction, e.g., sodium will be summarized as hyponatremia and hypernatremia.

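### Section 7.1 and the Table 7-5 note leave AE reporting of abnormal on-treatment electrolytes to discretion, against the mandatory rule in 7.2.2.5 and 8.1, so some AE-based counts may be incomplete

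*Protocol*

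**What the plan says.** **The discretionary rule.** Protocol Section 7.1 has electrolytes checked at the start of each of the first six cycles, and later as clinically indicated. It then says "The results should not be captured in clinical database" and "Eventual abnormal electrolyte lab results should be reported as AEs at the investigator's discretion". The scheduled-visits note in Table 7-5 (Section 7.2.2.5) agrees: potassium, sodium, corrected calcium and magnesium "are to be monitored but are not captured in the eCRF", followed by "Abnormal electrolyte lab results should be reported as AEs at the investigator's discretion".

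**The mandatory rule.** The body text of the same Section 7.2.2.5 requires an AE entry for a laboratory abnormality that is clinically significant, causes signs or symptoms, needs concomitant therapy or needs a ribociclib dose adjustment. Section 8.1.1 defines laboratory AEs in nearly the same terms. Section 8.1.2.1 covers a dose hold or medication that the protocol itself requires, "in which case the lab abnormality would still, by definition, be an adverse event and must be reported as such".

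**Where the protocol requires a hold.** Table 6-5 step 2 applies at every QTcF grade and calls for interruption and correction when electrolytes are out of range. Section 6.3.1.3.5, for other adverse reactions that may involve electrolyte imbalance, says: "If electrolyte values are outside of the normal range, interrupt ribociclib administration, correct electrolytes with supplements or appropriate therapy as soon as possible".

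**The concern.** The note and the AE definition govern the same result and give different instructions. A low potassium that leads to a ribociclib hold and a supplement is an AE under Section 8.1, but under the note it is one only if the investigator so chooses. The note is more specific and sits in the laboratory schedule, so a site could reasonably follow it.

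For blood counts and liver tests, a missed AE would still show in the CTCAE-graded laboratory tables, because the values are stored. On-treatment electrolytes have no such backstop. SAP 5.3 describes programmatic grading and uses sodium as its example ("sodium will be summarized as hyponatremia and hypernatremia"), but only screening values could feed it.

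The AE page supplies the primary endpoint categories (Protocol 10.4.1, SAP 2.5.1), including Grade 3/4 AEs and AEs leading to dose reduction or interruption. Protocol 10.5.3.6 defines tolerability as reductions or interruptions due to an AE. Electrolytes also bear on QT prolongation, an AE of special interest. Section 1.2.1.2.1 cites a sudden death "reported as treatment-related in a patient that had grade 3 hypokalemia and grade 2 QTcF prolongation".

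**Working it through.** **1. Do the rules collide, or cover different results?**

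| Result | Section 7.1 / Table 7-5 note | Sections 7.2.2.5, 8.1.1, 8.1.2.1 |
|---|---|---|
| Abnormal, no hold, no therapy, no symptoms | Discretion | AE only if judged clinically significant: compatible |
| Abnormal, supplement given | Discretion | AE: conflict |
| Abnormal potassium, calcium or magnesium in a QTcF work-up (Table 6-5) or an electrolyte-related reaction (6.3.1.3.5), ribociclib held | Discretion | AE, even though the protocol prescribes the hold: conflict |

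The note has no exception for the last two rows. Sodium is in the note but not in the two hold provisions, so for sodium the conflict arises only through therapy, symptoms, significance or another treatment change.

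**2. Which counts are exposed?**

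- *Any AE:* barely. SAP 2.8.1 counts each patient once per category. The hold provisions start from a QTcF finding or another adverse reaction, and neutropenia alone affected 74.3% in the ribociclib arm of the phase III trial cited in Section 1.2.1.2.1.
- *Electrolyte preferred terms and Grade 3/4 AEs:* exposed, since they rest on the AE page alone.
- *AEs leading to dose reduction or interruption:* partly exposed. At QTcF of 481 ms or more, Table 6-5 already interrupts ribociclib for the QTcF finding. At 450-480 ms it asks for no dose adjustment for the QTcF itself, so a step 2 hold would rest on the electrolyte, and an unreported electrolyte AE would drop that interruption from the category.
- *All interruptions:* not exposed. Section 6.3.1 requires each one on the Dosage Administration Record (DAR), and SAP 2.4.1.5 counts interruptions and reasons from there.
- *QT events:* not exposed. SAP 2.8.2 and 2.8.5.1 count QT AEs and QTcF categories without reference to electrolytes.

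**3. Size.** The plan's own figure reproduces: for a 0.1% AE rate and 3,000 patients (Protocol 10.8), 1 − (1 − 0.001)^3000 = 95.03%, against 95.0% stated.

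The documents give no rate of qualifying electrolyte abnormalities and no reporting fraction, so the under-count cannot be computed. As illustration only, assume a share r of qualifying events is reported. The chance of seeing at least one event at a true rate of 0.1% is then 1 − (1 − 0.001r)^3000:

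| r (assumed) | P(at least 1) |
|---|---|
| 1 | 95.0% |
| 0.9 | 93.3% |
| 0.75 | 89.5% |
| 0.5 | 77.7% |
| 0.25 | 52.8% |

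For a commoner event, assume a true rate of 3%, or 0.03 × 3,000 = 90 patients. At r = 0.9, 81 are reported, with an exact 95% interval of 2.15% to 3.34%, which still contains 3%. At r = 0.5, 45 are reported, with an interval of 1.1% to 2.0%, which excludes it. At r = 1 nothing is lost.

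**4. QT attribution.** At the 3.3% rate of QTcF above 480 ms in Section 1.2.1.2.1, 0.033 × 3,000 = 99 patients would have an event with no planned on-treatment electrolyte value in the database. Table 7-5 does list screening electrolytes as collected.

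**The case against.** The best defence is that the rules can be read together. The mandatory rule stands in the same section as the note and points to 8.1, clinical significance is itself an investigator judgement, and Section 8.1.2.1 says abnormalities that are not AEs should not be reported. Discretion would then apply only to results needing no hold or therapy, and a site applying 8.1 would lose nothing. This shows that loss is not inevitable. It does not remove the conflict, because the note covers abnormal electrolyte results without limit.

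The second defence is that other records allow a check. Interruptions and reasons are on the DAR, and supplements must be entered as concomitant medication (Section 6.4.1), so a hold plus a supplement with no matching AE could be noticed. This stands for the Core Phase. It is weaker in the Extension Phase, which 415 patients had entered by Amendment 04: Table 7-2 collects concomitant medication only when related to an AE or SAE, so an unreported AE can take its supplement record with it. Table 7-2 schedules no electrolyte tests either, so fewer such results would arise there.

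The third defence is that non-capture was deliberate. The Amendment 02 log lists the note as a clarification, and no planned analysis relates QTcF to electrolytes. This also stands, so storing the values is a design preference and not a correction.

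Three stronger readings are tempting, and the documents do not support them:

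- *Primary AE and interruption counts are under-recorded.* No under-count is shown, and total interruptions do not depend on the AE page.
- *QT events cannot be interpreted.* They can be counted and graded. What is limited is database-level attribution to the electrolyte level at the time.
- *About 99 patients would have a QT event and no electrolyte value at all.* Screening values are among the collected parameters.

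**Conclusion.** The conflict is real and should be reconciled. Because on-treatment electrolyte values are not stored, an AE omitted under the discretionary wording cannot be recovered by programmatic grading. Electrolyte preferred-term counts, Grade 3/4 counts and the category of AEs leading to dose reduction or interruption may therefore be incomplete.

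The size is unknown and could be zero. It equals the share of mandatory electrolyte AEs that sites treat as optional, which the documents do not give. The illustrative figures rest wholly on assumed reporting shares and, in the second example, an assumed event rate. No hypothesis is tested, and no sample size or precision figure in the plan changes.

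SAP 5.3 adds little to the case. Sodium is an example within a general grading rule there, and the SAP does not specifically promise an on-treatment electrolyte table.

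**What to change.** In Section 7.1 and in the Table 7-5 note, replace the discretion sentence with: *Electrolyte abnormalities meeting the criteria in 8.1.1/8.1.2.1 must be reported as AEs; other abnormalities need not be.* This changes AE reporting only and leaves the dosing guidance untouched.

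The cost is two sentences of protocol text and a slightly higher AE count. Amendment 04 states that the Core Phase is complete, so a change to this version acts on Extension Phase reporting and does not alter what Core Phase sites have already entered.

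Optional only: list the electrolytes already drawn in the work-up of QTcF of 481 ms or more beside the QTcF value. At the quoted 3.3% rate this concerns about 99 patients, whose results should be in source documents (Section 9.2). It would help attribution of QT events, but no planned analysis needs it.

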7.2.2.5.1 Hematology

Hematology tests are to be performed according to the Visit Evaluation Schedules outlined in Table 7-1. For details of the Hematology panel refer to Table 7-5.

7.2.2.5.2 Clinical chemistry

Chemistry tests are to be performed according to the Visit Evaluation Schedules outlined in Table 7-1. For details of the Chemistry panel refer to Table 7-5.

7.2.2.5.3 Coagulation

INR is to be performed according to the Visit Evaluation Schedules outlined in Table 7-1.

7.2.2.5.4 Pregnancy and Hormonal Levels

Pregnancy tests are to be performed according to the Visit Evaluation Schedules outlined in Table 7-1 and Table 7-2

A positive urine test is required to be confirmed by an immediate serum pregnancy test.A positive pregnancy test requires immediate interruption of study treatment until the assessment is confirmed. If positive, the patient must be discontinued from the study.

FSH and estradiol will be collected locally and used for screening and confirmation of menopausal status and clinically monitored as indicated. FSH and estradiol results are not recorded in the eCRF.

7.2.2.6 Cardiac assessments

7.2.2.6.1 Electrocardiogram (ECG)

Standard 12 lead ECG assessments will be performed locally at screening, C1D15, C2D1, and thereafter as clinically indicated, and EOT visit (see Table 7-1). There will be no central review of ECGs. QT interval corrected by Fridericia's formula (QTcF) will be used in this trial for trial eligibility and safety assessments.

If an abnormal ECG or QTcF value of \geq 481 ms is obtained at any time after C1D1, study treatment must be interrupted, repeat ECG and follow management guidelines detailed in Table 6-5.

An unscheduled ECG may be repeated at the discretion of the investigator at any time during the study and as clinically indicated. Local cardiologist ECG assessment may be performed at any time during the study at the discretion of the investigator.

Interpretation of the tracing must be made by a qualified physician and documented on the ECG eCRF page. Each ECG tracing should be labeled with the study number, patient initials (where regulations permit), patient number, date, and kept in the source documents at the study site. Clinically significant abnormalities present when the patient signed informed consent should be reported on the Medical History eCRF page. Clinically significant findings must be discussed with Novartis prior to enrolling the patient in the study. New or worsened clinically significant findings occurring after informed consent must be recorded on the Adverse Events eCRF page.

